## 11.9 Nasal Fluid Samples for Biomarkers

Nasosorption with synthetic absorptive matrices (SAM) have been used to sample nasal mucosal lining fluid [16]. This technique can be considered as "precision mucosal sampling", since it samples directly from the respiratory mucosa, and is free from the salivary contamination that occurs in breath and sputum sampling. Nasosorption sampling involves manipulating the synthetic absorptive matrix (SAM) up the lumen of the nasal cavity, and then holding it in position against the mucosa by external firm finger pressure. This is more comfortable and less invasive than using a conventional swab, where rotation against the mucosal surface is generally required.

Nasosorption will be performed by placing strips of a hydrophilic polyester absorptive matrix

(Mucosal Diagnostics, Hunt Developments Ltd., Midhurst, UK: available as a CE-marked device) measuring  $7 \times 35$  mm into each nostril for 1 min. When the SAM strip is removed, it may be placed back in to its container and frozen at  $-80^{\circ}$ C until shipment to a designated central lab for biostorage, elution, and testing. After shipment to a designated lab, SAM strips will be washed in P B S b u f f e r p H 7 . 4 (100 µ l) c o n t a i n i n g cup of a spin filter insert (Costar® Spin-X®). Mucosal lining fluid will be then eluted from the SAM by spin filter centrifugation (5 min at 16,000G at 4 °C), left and right nostril samples combined, and aliquots tested for biomarkers to evaluate the immune response.

Nasal fluid for biomarkers will be collected at Randomization (end of 4 week baseline period; V3), Prevention Treatment Week 4 (V4), Prevention Treatment Week 8 (V5), Prevention Treatment Week 12 (V6), and Follow-Up Week 16 (End of Study; V7) according to Appendix A. Samples will also be collected in the event of an Unanticipated/Early Termination Visit.

Samples may be evaluated for select biomarkers that may include several of the following as well as others:

1. Inflammatory cytokines/chemokines/immune cell markers/neuropeptides: IL-1beta, IL-2, IL-4, IL-5, IL-6, IL-8, IL-9, IL-10, IL-12p40, IL-12p70, IL-13, IL-15, IL-16, IL-17, IL-18, TNF-alpha, GM-CSF, MIP-1 alpha, MIP-1 beta, MCP-1, Eotaxin-1, MDC, PGD2, beta-tryptase, histamine, C3a/C4a/C5a, LTC4, MMP9, CGRP

Optionally, samples may be evaluated for nasal microbiome (e.g., PCR) to confirm presence of B244.

## 11.10 Study Diary

Subjects will be asked to fill out a daily migraine-history diary from screening to treatment with study drug and a migraine-treatment diary from treatment through the remainder of the follow-up period. Study diary will be electronic using an electronic patient reported outcomes (ePRO) device.

Study diary entries will be daily and will include recording of migraine frequency, duration, and severity that includes information on migraine days (experiencing migraine with or without aura in a given day), headache days (experiencing headache in a given day), migraine intensity, migraine duration, headache intensity, and headache duration. Additional patient reported outcomes may include recording of nausea, vomiting, photophobia, and sonophobia, as well as information about the headache in the trial (i.e., headache intensity, presence/absence of associated symptoms, unilateral/bilateral location, aggravation by exercise, throbbing/non-throbbing) to verify migraine headache symptoms. Subjects will also record their use of rescue (acute migraine specific) medications and dosing administration. The diary will ask the subjects about their headache which will allow the patients' responses to determine whether that headache is migraine or not.

The following definitions will be used for determination of migraine, migraine days, and other inclusion/exclusion criteria:

BSA

### **Episodic migraine:**

• No more than 14 headache days per month and for this study at least 4 of those days must be migraine days.

## Migraine without aura (per International Headache Society [IHS] 1.1 criteria):

- Headache attacks lasting 4-72 hours
- At least 2 of the following:
  - o unilateral location
  - o pulsating quality
  - o moderate or severe pain intensity
  - o aggravation by or causing avoidance of routine physical activity
- At least one of the following
  - o nausea and/or vomiting
  - o photophobia and sonophobia

## Migraine with aura (IHS 1.2):

- Migraine associated with one or more of the following fully reversible aura symptoms: visual, sensory, speech and/or language, motor, brainstem, retinal.
- At least 3 of the following:
  - o At least one aura symptoms spreads gradually over >5 min
  - o 2 or more aura symptoms occur in succession
  - Each individual aura symptoms lasts 5-60 min
  - At least one aura symptom is unilateral
  - o At least one aura symptom in positive
  - o The aura is accompanied or followed within 60 min by HA

#### Migraine day:

- Migraine day is defined as any calendar day in which the subject experiences a qualified migraine headache (onset, continuation, or recurrence of the migraine headache). It is a self-reported headache which meets the IHS criteria for migraine with or without aura or probable migraine. A probable migraine is defined as a headache that meets only 2 of the 3 criteria (listed in the migraine without aura definition).
- If the patient uses a migraine specific medication such as a triptan, that will be counted as a migraine day no matter how short the headache attack is as long as it's at least 30 minutes.
- Migraine day will be determined from a 24 hour period from 12 am to 11:59 pm each day.

#### Headache day:

A non-migraine headache day.

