#### 2 INTRODUCTION

## 2.1 Background

Migraine is a chronic, recurrent disorder affecting an estimated 37 million Americans. Migraine is marked by recurring moderate to severe headache with throbbing pain that usually lasts from 4-72 hours, typically unilateral in location, is often accompanied by nausea, vomiting, and sensitivity to light or sound, and is sometimes preceded by an aura and is often followed by fatigue. Around 12% of adults have episodic migraine (headaches on less than 15 days per month) [3], while around 1% of the adult population suffers from migraine and headaches on more days than not [4], a condition termed chronic migraine. In addition, during a migraine attack, individuals experience impaired health-related quality of life and considerable disability [5, 6].

The treatment of migraine consists of acute/abortive therapies and preventive therapies. The acute treatment of migraine includes most commonly, migraine-specific medications such as triptans and ergotamines which, while effective in a majority of cases may be limited by side effects, the development of medication overuse/rebound and some contraindications including cardiovascular, cerebrovascular and peripheral vascular disease and hypertension. Preventive treatments include four medications approved by the FDA for migraine prevention: anti-epilepsy medications topiramate and divalproex sodium; and beta-adrenergic blockers propranolol and timolol. These drugs are not disease-specific and are plagued by a plethora of tolerance issues including cognitive side effects, weight loss or weight gain, depression, hypotension, etc., and therefore adherence to therapy is typically low. Botulinum Toxin A is approved for the narrow indication of chronic migraine prevention but is expensive and requires multiple injections in the face, scalp and neck. In addition, nearly half of individuals with episodic or chronic migraine who are in need of preventive therapies do not receive them [7].

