#### 6.3 Inclusion Criteria

Deviations from inclusion criteria are not allowed because they can potentially jeopardize the scientific integrity of the study, regulatory acceptability or participant safety. Therefore, adherence to the criteria as specified in the protocol is essential.

Participants eligible for enrollment in the study must meet all the following criteria:

- 1. Males and Females, 18 to 65 years of age.
- 2. In good general health as determined by a thorough medical history and physical examination, and vital signs.
- 3. At least a 1-year history of migraine with or without aura that began before the age of 50 years old and consistent with a diagnosis of migraine with or without aura according to the International Classification of Headache Disorders, 3rd edition, beta version.
- 4. Experiences 4-14 migraine days per month and 3-14 migraine attacks per month and no more than 14 headache days per month (including migraine and non-migraine headache days) in the 3 months prior to screening.
- 5. Experiences 4-14 migraine headache days per month during the baseline period.
- 6. Ability and willingness to abstain from taking medications not allowed by the protocol or administering any foreign substance intranasally.
- 7. Ability and willingness to complete a migraine-history diary from screening to treatment with study drug and a migraine-treatment diary from prevention treatment through the remainder of the follow-up period.

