#### 6.4 Exclusion Criteria

Deviations from exclusion criteria are not allowed because they can potentially jeopardize the scientific integrity of the study, regulatory acceptability or participant safety. Therefore, adherence to the criteria as specified in the protocol is essential.

Participants will be excluded from the study if any of the following criteria are met:

- 1. Headache on greater than 14 days/month in any of the three months (90 days) preceding entry into the study.
- 2. Use of acute migraine-specific medications (e.g., ergotamine, triptan) on more than 10 days per month in the previous 3 months and during study.
- 3. Use of intranasal migraine medications during study.
- 4. Use of any intranasally administered over-the-counter product or nasal irrigation (e.g., neti pot) during study.
- 5. Opioids/barbiturates used on more than 4 days per month in the previous 3 months and throughout the duration of the study.
- 6. Use of analgesics (including acetaminophen, nonsteroidal anti-inflammatory drugs [NSAIDs], acetylsalicylic acid, or combination analgesics) for migraine or non-migraine headaches on more than 14 days per month in the previous 3 months and during study.
- 7. Use of migraine prevention medication within two months prior to study and throughout the duration of the study.
- 8. Botulinum toxin injection within 3 months prior to screening or during study.
- 9. Anti-CGRP monoclonal antibody (e.g., erenumab, fremanezumab, galcanezumab, and eptinezumab) injection or infusion within 4 months prior to screening or during study.
- 10. Small molecule anti-CGRP medications in the 30 days prior to the screening visit.
- 11. Use of systemic antibiotics during study.
- 12. Pregnancy or breast-feeding.
- 13. Female of childbearing potential not using adequate contraceptive measures.
- 14. Inability to give informed consent.
- 15. History of neurological, psychiatric, or any other medical condition that in the opinion of the investigator may compromise the subject's ability to safely participate in the study.
- 16. Subjects with any significant clinical abnormalities which may interfere with study participation.
- 17. Prior use of AO+ Mist
- 18. Subjects with immunodeficiencies, nasal lesions, nasal polyps, or sinus infections.
- 19. Subjects who have participated in an investigational drug trial in the 30 days prior to the screening visit.
- 20. Inability to maintain at least 80% diary compliance during the study from baseline to follow-up.

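### Protocol section 11.10 defines a headache day as a non-migraine day, contradicting its own text and stripping migraine days from the headache-day endpoint if applied

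*Protocol*

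**What the plan says.** Section 11.10 (Study Diary) handles the term in three ways.

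- The description of diary entries lists "headache days (experiencing headache in a given day", that is, any day with headache.
- The definition of episodic migraine reads "No more than 14 headache days per month and for this study at least 4 of those days must be migraine days". Migraine days are a subset of headache days here.
- The entry headed *Headache day* reads "A non-migraine headache day".

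The list of definitions is introduced with this sentence: "The following definitions will be used for determination of migraine, migraine days, and other inclusion/exclusion criteria". Endpoints are not named in it.

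Elsewhere the inclusive sense prevails. Inclusion criterion 4 (section 6.3 and the Clinical Trial Summary) sets a limit of "no more than 14 headache days per month (including migraine and non-migraine headache days". Exclusion criterion 1 (section 6.4) needs no defined term: "Headache on greater than 14 days/month in any of the three months (90 days) preceding entry into the study". The Background (section 2.1) describes "episodic migraine (headaches on less than 15 days per month" in the same inclusive way.

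Change in monthly headache days is a secondary endpoint (section 4.2, section 13 and the Clinical Trial Summary). It is one of the continuous endpoints compared between arms by the one-sided z-test (sections 13 and 14.5). None of these places says which days count.

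**The concern.** The only headed definition of the term contradicts two statements in its own section and the eligibility criterion that uses it. Whoever derives the headache-day endpoint and looks for a definition will find one entry under that name, and it leaves out every migraine day.

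For a preventive migraine treatment this matters. An endpoint built that way cannot register a prevented migraine day. It also scores partial benefit, where a migraine becomes a milder non-migraine headache, as harm. If the conflict is left until results are available, someone will have to choose between two readings that can give different answers.

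**Working it through.** **1. Can the definitions hold together?** Under the headed definition no headache day can be a migraine day, so the number of headache days that are migraine days is 0. The definition of episodic migraine requires at least 4. No subject could satisfy both, so at least one of the two is wrong as written. The diary description and inclusion criterion 4 both side with the inclusive reading, and the headed entry is the outlier.

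**2. Is eligibility affected?** No. Inclusion 4 states its own inclusive meaning, exclusion 1 counts days with headache directly, and the baseline criterion is set on migraine days: "Experiences 4-14 migraine headache days per month during the baseline period".

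**3. What happens to the endpoint?** Let M be migraine days and H non-migraine headache days per month, with each day that has headache classed as one or the other.

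- Inclusive count: M + H
- Headed definition: H alone

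Two subjects with assumed counts show the effect:

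| Baseline (M, H) | Later (M, H) | Inclusive change | Headed-definition change |
|---|---|---|---|
| 8, 3 | 4, 3 | 7 − 11 = −4 | 3 − 3 = 0 |
| 8, 3 | 4, 5 | 9 − 11 = −2 | 5 − 3 = +2 |

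**4. Difference between arms.** The protocol gives no effect or standard deviation for headache days, so there is no figure of its own to reproduce and no power can be computed. It does give assumed reductions in migraine days (Clinical Trial Summary, Sample Size): 3.8 on active and 2.3 on placebo, so active minus vehicle is −3.8 − (−2.3) = −1.5.

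Two quantities are assumed, because the protocol states neither:

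- s: share of avoided migraine days that remain as non-migraine headache days, equal in both arms
- d: direct drug effect on other non-migraine headache days (negative is favourable)

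Active minus vehicle is then:

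- Headed definition: 3.8s − 2.3s + d = 1.5s + d
- Inclusive: −1.5 + 1.5s + d = −1.5(1 − s) + d
- Gap: (1.5s + d) − (−1.5 + 1.5s + d) = 1.5 for every s and d

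| s | d | Inclusive | Headed definition |
|---|---|---|---|
| 0 | 0 | −1.5 | 0 |
| 0.25 | 0 | −1.125 | +0.375 |
| 0 | −0.5 | −2.0 | −0.5 |
| 0.5 | −0.5 | −1.25 | +0.25 |

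Under the headed definition the endpoint favours B244 only if d < −1.5s.

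**5. Room to improve.** Inclusion 5 allows 4 to 14 migraine days at baseline. If the cap of 14 headache days also holds in the baseline month (an assumption, since inclusion 5 caps migraine days only), H is at most 14 − M: 10 for M = 4, 5 for M = 9 and 0 for M = 14. Baseline values then run from 4 to 14 on the inclusive count and from 0 to 10 on the headed one, and a subject with 14 migraine days starts at 0 and cannot improve. Without the cap, that subject could still have non-migraine headache days.

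**The case against.** The strongest reply is that the harm is conditional and the text leans against it. The lead-in confines the list to migraine, migraine days and eligibility, and the diary item that would feed the endpoint is described inclusively. A heading gives an entry no precedence, so a careful analyst would probably use the inclusive count. That is fair, and it is why the effect on the endpoint is stated as a risk. It does not rescue the entry: within the scope the lead-in does claim, the entry contradicts both inclusion 4 and the definition of episodic migraine.

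A second reply is that derivation of a secondary endpoint belongs in a statistical analysis plan. That would answer a complaint about missing detail, but this is a stated definition that is wrong. An analysis plan that copies it inherits the error, and one that departs from it conflicts with the protocol.

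Third, a non-migraine count could be a deliberate complement to the migraine-day endpoint. Nothing in the protocol says so. If it is the intent, the endpoint needs that name.

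Fourth, the 1.5-day gap is an identity that restates the assumed migraine-day effect, and s and d are not protocol figures. Both points stand. The table shows direction under stated assumptions and does not estimate bias.

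Finally, the endpoint on moderate and severe headache days uses the same term. That also stands. Its reference to the migraine pain-intensity score may tie it to migraine pain, but the protocol does not settle this, so a second endpoint may be exposed.

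**Conclusion.** The point holds: the headed definition in section 11.10 is wrong as written and should be corrected. That conclusion rests on the text alone.

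The consequence is limited. It reaches the secondary endpoint on monthly headache days, and possibly the one on moderate and severe headache days, and only if the headed definition is applied to them. In that case the between-arm difference in monthly headache days shifts against B244 by the full migraine-day effect, 1.5 days per month on the protocol's planning values. Whether the sign reverses depends on the assumed s and d.

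The primary safety endpoint, the migraine-day and responder endpoints, the eligibility criteria and the sample size are unaffected, and no data are lost.

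**What to change.** In section 11.10, define *Headache day* as any calendar day with a headache of any type: migraine, probable migraine or non-migraine. Where the narrower count is wanted, call it *non-migraine headache day*. Add a sentence stating that the monthly headache-day endpoint uses the inclusive definition, and say in the same place which days the moderate-and-severe headache-day endpoint counts. Do this before unblinding.

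The cost is one definition line and a sentence or two on the endpoints. No new data are needed, because the diary already records migraine days and headache days (section 11.10; Appendix A, footnote 12).

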#### Migraine attack:

• An episode of any qualified migraine headache. To distinguish an attack of long duration from two attacks or to distinguish between attacks and relapses:

- o A migraine attack that is interrupted by sleep, or temporarily remits, and then recurs within 48 hours (i.e., <48 hours between the start of the migraine attack to the time of the recurrence) will be considered as one attack and not two.
- An attack treated successfully with medication but with relapse within 48 hours (i.e., <48 hours between the start of the migraine attack to the time of recurrence) will be considered as one attack.

Subjects will be advised to record their diary in the evening (after the night time dose) as a 24 hour reflective diary entry. For missed diary entries, subjects will be allowed to record up to 48 hours retrospective data. Subjects will be encouraged to record at least 80% of the daily diary days (80% diary compliance) during the study (from baseline to end of follow-up period) to remain on the study.

## 11.11 Migraine Pain Intensity Score

International Headache Society guidelines for the conduct of controlled trials of headache treatments recommend the use of the 4-point verbal rating scale (VRS) to measure pain intensity.

Migraine pain intensity score will be recorded daily in the study diary at the times indicated in the Schedule of Events Table (Appendix A) beginning at Screening (V1) and daily until Follow-Up Week 16 (End of Study; V7). More specifically, daily assessments of migraine severity will be recorded in the study diary during screening, the baseline period (Day -28 to 0), prevention treatment period (Day 0 to 84), and follow up observation period (Day 84 to 112).

4-point VRS scale for pain intensity is as follows:

0 = no pain

- 1 = mild pain (bothersome but not interfering with normal function)
- 2 = moderate pain (interfering with normal function)
- 3 = severe pain (requiring bedrest and unable to function)

#### **11.12 MIDAS**

Migraine Disability Assessment (MIDAS) questionnaire will be administered at the times indicated in the Schedule of Events Table (Appendix A): Baseline (beginning of 4 week baseline period; V2), Randomization (end of 4 week baseline period; V3), Prevention Treatment Week 12 (V6), and at Unanticipated/Early Termination Visit should one occur. The participant will answer a questionnaire examining the relationship between impact of migraine and quality of life.

MIDAS questionnaire can be found in Appendix B.

#### 11.13 HIT-6

Headache Impact Test-6 (HIT-6) questionnaire will be administered at the times indicated in the Schedule of Events Table (Appendix A): Baseline (beginning of 4 week baseline period; V2), Randomization (end of 4 week baseline period; V3), Prevention Treatment Week 4 (V4),

Prevention Treatment Week 8 (V5), Prevention Treatment Week 12 (V6), Follow-Up Week 16 (End of Study; V7), and at Unanticipated/Early Termination Visit should one occur. The participant will answer a questionnaire examining the relationship between impact of migraine and quality of life.

HIT-6 questionnaire can be found in Appendix C.

## 11.14 MSQL

Migraine Specific Quality of Life (MSQL) questionnaire will be administered at the times indicated in the Schedule of Events Table (Appendix A): Baseline (beginning of 4 week baseline period; V2), Randomization (end of 4 week baseline period; V3), Prevention Treatment Week 4 (V4), Prevention Treatment Week 8 (V5), Prevention Treatment Week 12 (V6), Follow-Up Week 16 (End of Study; V7), and at Unanticipated/Early Termination Visit should one occur. The participant will answer a questionnaire examining the relationship between impact of migraine and quality of life.

MSQL questionnaire can be found in Appendix D.

#### 11.15 CGI

Clinical Global Impression (CGI) scale is an investigator assessment that will be administered at the times indicated in the Schedule of Events Table (Appendix A): Baseline (beginning of 4 week baseline period; V2), Randomization (end of 4 week baseline period; V3), Prevention Treatment Week 4 (V4), Prevention Treatment Week 8 (V5), Prevention Treatment Week 12 (V6), Follow-Up Week 16 (End of Study; V7), and at Unanticipated/Early Termination Visit should one occur. The clinician will assess measures of symptom severity, treatment response and the efficacy of treatments in patients.

CGI scale can be found in Appendix E.

